5.3.2 Safety outcomes

Please see Section 6.2 on Harms for definitions of the safety outcomes. Adverse events, adverse reactions, serious adverse events, serious adverse reactions and suspected unexpected serious adverse reactions will be summarised overall and by treatment group as counts of events and counts of people who have had events. We will calculate differences in event rates between the two groups and a 95% confidence interval for the difference.

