3.5 Duration of the study and participant timeline

Study duration: the study is funded for 38 months (November 2016 to December 2019). The initial Development Phase will run for 11 months, from November 2016 to September 2017. The feasibility RCT will run for 29 months, from October 2017 to December 2019. Enrolment to RCT will last for 13 months (October 2017 to November 2018).

Duration of participant involvement: participants allocated to the intervention arm will be in the study for approximately 6 months from recruitment; participants allocated to the wait-list control condition for approximately 9 months. Below is a detailed description of the participant timeline during the feasibility RCT.

Participant Timeline

Purpose	Person responsible	Time	Forms/ Measures	Description	Arm of trial
Identification	SLT (via NHS); Self-identified (via community)	10 minutes	Initial information one-page sheet	Potential participants identified, and asked permission for their contact details to be passed to research team.	All
Information giving	Cl	15 minutes	Full Participant Information Sheet	CI to send potential participant PIS at least 24 hours prior to visiting.	All
Information giving and consent	CI	60 minutes	PIS; consent form	CI to visit potential participant (location of participant's choice) and discuss the project, going through the PIS in detail. Written consent to be obtained.	All
T1 Assessment and baseline profiling	RA	50 minutes	FAST; WEMWBS; DISCS; GHQ-12; CPIB; EQ-5D-5L; case history	Outcome measures completed in interview format. FAST at baseline only.	All
Randomisation	CI	10 minutes		Letter, visit or phone call (participant preference) to inform them of group allocation.	All
Intervention	Trial clinicians	6 visits (each visit about 60 minutes)		SFBT therapy sessions	Intervention Arm
T2 Assessment (3 months post randomisation)	Blinded RA	30 minutes	WEMWBS; DISCS; GHQ-12; CPIB; EQ-5D-5L	Face-to-face visit to conduct assessments	All
T3 Assessment (6 months post randomisation)	Blinded RA	30 minutes	WEMWBS; DISCS; GHQ-12; CPIB; EQ-5D-5L	Face-to-face visit to conduct assessments	All
T3 in-depth interview	Unblinded RA or Cl	60 minutes	topic guide; SRS	Face-to-face interview	All
T3 resource use questionnaire	CI	20 minutes	Adapted CSRI	Optional additional visit	All
Intervention	Trial clinicians	6 visits (each visit about 60 minutes)		SFBT therapy sessions	Wait-list control arm

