3.6 Sample size

For the feasibility RCT, we will recruit 32 participants in total, 16 participants allocated to each arm of the project. If around 15% are lost to follow up¹⁴, we anticipate that around 28 will be followed up at 6 months. This sample is adequate to inform the parameters of a larger trial, such as recruitment rates, consent rates, completion rates, acceptability, and potentially effect size of outcome measures⁵².

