6.2 Harms

Adverse Events (AE) are any clinical change, disease or disorder experienced by the participant during their participation in the trial, whether or not considered related to the intervention being investigated. Adverse Events associated with participating in the study are considered unlikely. Such adverse events may include participants becoming distressed or anxious during assessment or therapy sessions, or during the in-depth interview.

Adverse events not related to the study may include:

Participants reveal to RAs or trial clinicians unrelated new medical issues which require an
assessment by a healthcare professional (e.g. fits or seizures, worsening visual difficulties,
increased frequency or severity of headaches, accidents or injuries such as falls).

Participant may score as 'distressed' on the GHQ-12 (scoring over 3) indicating low mood at any of
the assessment points; or may discuss symptoms of depression or anxiety during therapy sessions
or the in-depth interview.

Risks arising in the home or within the family.

If these adverse events do not lead to any of the outcomes listed a-g below, they will be considered non-serious. Their reporting is covered in the next section. RAs and trial clinicians will be trained on how to respond to such events (see 6.2.2 below).

Serious Adverse Events (SAEs) are considered unlikely in this project, however, they may still occur. Strokerelated events will not be reported as SAEs because these are expected within this population. An AE is considered a SAE if it results in one of the following outcomes:

- a) Death
- b) Suicide
- c) Life-threatening (i.e. with immediate, not hypothetical, risk of death at the time of the event, e.g. further stroke, cardiovascular event, serious infection)
- d) Requires in-patient hospitalisation (hospitalisation for elective treatment of a pre-existing condition is not included)
- e) Increased severe and persistent disability, where severe indicates significant deterioration in the participant's ability to carry out their activities of daily living; and persistent indicates four weeks continuous duration.
- f) Any other important medical condition, which, though not included in the above, may jeopardise the participant and may require medical or surgical intervention to prevent one of the outcomes listed.
- g) Any episode of deliberate self-harm

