6.2.1 Reporting AEs, SAEs, SARs and SUSARs

AEs (including SAEs, SARs and SUSARs) may be identified by RAs, the trial clinicians, the qualitative RA or the CI. All research staff will be responsible for reporting of AEs (including SAEs, SARs, and SUSARs) throughout the project.

All adverse events will be recorded on forms, and emailed to the CI within 24-48 hours of occurrence. The SAE form includes the potential outcomes (a-g above) to facilitate research staff choosing between the AE and SAE forms. Research staff will also receive training in completing the forms and handling AEs. The forms will be completed as thoroughly as possible with all available details of the event. In the case of incomplete information at the time of initial reporting, the research staff member will still notify the CI as quickly as possible, and provide subsequent additional information as it becomes available. A record of this notification (including date of notification) will be clearly documented to provide an audit trail.

All AEs (non-serious) will be reported to the Academic Supervisory Group on a monthly basis by the CI. These events will be reported to the TSC on an annual basis (or more frequently if requested) and will be included in the safety reporting of the completed trial.

For all SAEs (including SARs and SUSARs) the CI will notify a member of the Academic Supervisory Group within 24 hours. The relationship of the event to the treatment (SAE or SAR) and expectedness of the event (SAR or SUSAR) may be assessed and indicated on the form by the research staff member. The CI will discuss with at least two members of the Academic Supervisory Group whether the SAE is in fact a SAR or SUSAR.

The CI will also inform the research sponsor of SAEs. The Academic Supervisory Group and the sponsor will decide whether the SAE needs to be reported further to relevant regulatory bodies. If the SAE is considered by the CI and Academic Supervisory Group to be a SUSAR (i.e. related and unexpected), it will be reported to the Research Ethics Committee (REC) which approved the study, as per Health Research Authority (HRA) guidelines, using a modified version of the HRA non-CTIMP SAE report form.

Reporting timelines are as follows:

- SUSARs which are fatal or life-threatening must be reported not later than 7 days after the sponsor
 is first aware of the reaction. Any additional relevant information must be reported within a
 further 8 days.

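### The adverse event comparison in Protocol 5.3.2 needs a randomisation-to-T3 window: as written it takes in wait-list time on SFBT and GHQ-12 scores from before randomisation

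*Protocol*

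**What the plan says.** Protocol 5.3.2 has adverse events "summarised overall and by treatment group as counts of events and counts of people who have had events", and then adds: "We will calculate differences in event rates between the two groups and a 95% confidence interval for the difference". It states no start or end date for the comparison, no denominator, and no rule for wait-list time after T3. Section 5.3 makes intention to treat the primary basis of analysis, so events are counted under the randomised arm.

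Three other sections determine what enters that comparison:

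- **Which events count.** Section 6.2 defines an adverse event over the participant's whole time in the trial. Its examples include a GHQ-12 score over 3 at any assessment point; the same item continues "or may discuss symptoms of depression or anxiety during therapy sessions". T1 is an assessment point and comes before randomisation (2.3). Section 6.2.1 adds: "All research staff will be responsible for reporting of AEs (including SAEs, SARs, and SUSARs) throughout the project".
- **How long each arm is observed.** Section 3.5 says "participants allocated to the intervention arm will be in the study for approximately 6 months from recruitment", and "participants allocated to the wait-list control condition for approximately 9 months".
- **What the wait-list arm receives.** It is offered SFBT after T3 and is assessed again three months later at T4 (2.3, 3.5).

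Other outcomes do have a time point. The WEMWBS difference is taken at T3 (5.3.1), and costs come from the resource questionnaire at 6 months (5.3.4). Section 7.4 names safety of the intervention among the inputs to the decision on a definitive trial.

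**The concern.** A difference between randomised arms speaks to the safety of SFBT only if both arms are watched over the same period and one of them is not on SFBT. Read together, these sections meet neither condition. The wait-list arm has about half as much time again, one more GHQ-12 assessment, and a final three months on the therapy under test. Events in those months would be counted under usual care, which could make SFBT look safer than it is. GHQ-12 scores at T1 cannot be caused by allocation, yet they enter the event counts of both arms.

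What is at stake is how the safety table is read when a definitive trial is considered. No formal test or stopping rule depends on it.

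**Working it through.** **Plan's own figure.** The protocol gives no expected adverse event rate and no safety precision. The only related figure is the number followed up at 6 months (3.6): "we will recruit 32 participants in total, 16 participants allocated to each arm of the project", and "If around 15% are lost to follow up". This gives 32 × (1 − 0.15) = 27.2, against the stated figure of about 28, so it is reproduced to within one participant.

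**Inputs.** 16 per arm (3.6). About 6 and 9 months in the study (3.5). GHQ-12 at T1, T2 and T3 in both arms, and at T4 in the wait-list arm only (2.4, 3.5). 45% scoring as distressed in a comparable population (6.2.2). Assumptions: the 45% is constant over time, SFBT has no effect, and nobody drops out.

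**1. GHQ-12 events over full participation** = 16 × number of assessments × 0.45.

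- Intervention: 16 × 3 × 0.45 = 21.6
- Wait-list: 16 × 4 × 0.45 = 28.8
- Artificial difference: (28.8 − 21.6) / 16 = 0.45 events per person. It is 0.30 to 0.60 if the share is 30% to 60%.
- Arising at T1: 16 × 0.45 = 7.2 in each arm

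**2. Other adverse events.** The protocol gives no background rate, so a range is assumed, equal in both arms. Expected events = 16 × months × rate. Chance of at least one event = 1 − exp(−rate × months).

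| Rate per person-month | Events, 6 v 9 months | At least one event |
|---|---|---|
| 0.05 | 4.8 v 7.2 | 26% v 36% |
| 0.10 | 9.6 v 14.4 | 45% v 59% |
| 0.20 | 19.2 v 28.8 | 70% v 83% |

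**3. If rates are per person-month.** After randomisation, GHQ-12 events are 14.4 / (16 × 6) = 0.15 and 21.6 / (16 × 9) = 0.15, so unequal length no longer matters. If T1 scores stay in, the figures are 21.6 / 96 = 0.225 and 28.8 / 144 = 0.20, a small artefact that disappears when T1 is excluded. Counts of people still follow the last column of the table. Wait-list events during SFBT are still credited to usual care.

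**4. What T1 scores do to counts.** They are expected to be equal in the two arms, so they do not shift the difference in event counts. They do shrink a difference in people with an event. Take an assumed true 30% v 10%, independent of T1 status: 1 − 0.55 × 0.70 = 61.5% and 1 − 0.55 × 0.90 = 50.5%, so 20 points become 11.

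**5. After the fix.** From randomisation to T3, without T1, each arm has 16 × 2 × 0.45 = 14.4 expected GHQ-12 events and the difference is 0.

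**6. Contacts at which events may be found.** To T3 the intervention arm has at most 6 sessions + T2 + T3 + interview = 9, and the wait-list arm has 3. At the two sessions that 3.3.3 takes as compliance, it is 5 v 3. Over full participation the wait-list arm has up to 3 + 6 + 2 = 11, against 9. A T3 window therefore leaves a difference in contacts, which has to be described.

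**7. Precision.** The 95% half-width for a difference in proportions with 16 per arm is 1.96 × √(2p(1 − p)/16). For p = 0.20, 0.45 and 0.70 it is about 28, 34 and 32 points.

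**The case against.** The strongest reply is that the window belongs in the statistical analysis plan, which 5.3.1 promises and which is not shown here. Section 6.2 governs when events are recorded, not which of them enter the comparison, and a T3 limit would match the WEMWBS and cost analyses. This is fair, and that plan could settle the matter. But the definitions the protocol does state, applied as they stand, give the mixed comparison, so the protocol should not leave the window to inference.

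The reply on person-time also stands in part: if rates means events per person-month, unequal length is handled for rates. It does not help with counts of people or with SFBT exposure after T3.

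Four stronger readings are tempting, and the protocol does not support them:

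- **That the intervention arm would show two or three times as many events because it is seen more often.** Such a ratio needs session dates and a recall limit, and the protocol gives neither. Serious events in particular could still come to light at T2 or T3. The gap of 9 v 3 contacts is the maximum, and over full participation the count runs the other way.
- **That T1 scores favour one arm.** They precede randomisation, so in event counts they add noise and dilution, not direction.
- **That an efficacy outcome has been relabelled as harm.** Section 6.2 lists GHQ-12 scores among events not related to the study, 5.3.2 summarises adverse reactions as a class of their own, and 5.3.1 already summarises GHQ-12 by arm as a clinical outcome.
- **That events found in therapy sessions should be taken out of the comparison.** Distress in sessions is among the few study-related harms that 6.2 foresees, and removing it could hide the events most likely to be due to SFBT.

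**Conclusion.** The concern holds in a limited form. Followed as written, the safety comparison in 5.3.2 sets about 6 months against about 9, credits wait-list events during SFBT to usual care, and includes scores from before randomisation. With no effect of SFBT it would still show 21.6 v 28.8 GHQ-12 events. That figure assumes 45% positive at every assessment, full follow-up, and counting over all of participation.

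Severity is minor to moderate. The analysis is descriptive, seriousness and relatedness are judged case by case (6.2, 6.2.1), none of the pre-specified criteria in 3.4.1 concerns safety, and an interval of about ±28 to ±34 points could not carry a decision alone. The reason to act is that 7.4 will draw on this information and the correction is nearly free.

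**What to change.** In 5.3.2:

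1. Limit the between-arm difference and its confidence interval to events from randomisation to T3, and say whether a rate is per person or per person-month.
2. Tabulate wait-list events from T3 to T4 separately, labelled as occurring during SFBT.
3. Leave T1 GHQ-12 scores out of the adverse event comparison. Nothing is lost, because GHQ-12 is already summarised by arm at each time point.
4. Report events by where they were detected (therapy session or a visit common to both arms), and note that up to T3 the intervention arm has up to six more contacts. Keep session-detected events in the comparison.

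The GHQ-12 threshold is over 3 in 6.2 and 6.2.2 but 3 or more in 7.7. These passages must be reconciled, because the threshold decides what counts as an event.

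The cost is a few sentences, plus date and source of detection on the event form if they are not already there. The downside is that wait-list events after T3 are listed rather than compared. Event recording and the follow-up of distressed participants stay as they are.

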5.3.3 Qualitative analysis

Qualitative data will be reported according to the Standards for Reporting Qualitative Research Guidelines (SRQR). All interviews will be transcribed verbatim.

Analysis of qualitative data will inform Study Objectives One, Three, Four, Five, and Seven. The primary source will be in-depth interviews with all participants, and with therapists and Local Collaborators (at the end of the study). However, we will also refer to therapy and supervision records.

The data will be analysed using Framework Analysis²⁸. Initial themes and concepts will be identified through reviewing the data. These will then be used to construct a thematic index. All the interview material will then be indexed so that each phrase or passage can be assigned a label. Thematic charts will be constructed, the chart headings evolving from the indexing process. The labelled raw data will then be summarised and synthesised into the matrices. This matrix-based method of analysis enables systematic exploration of the range of views, and facilitates comparison both between cases and within cases to produce descriptive and explanatory accounts of the data. In order to minimise potential bias a second analyst will independently index a proportion of transcripts and analyse the matrix-based material to ensure all relevant thematic material is represented fairly and is included in the final framework.

5.3.4 Economic evaluation

Given the feasibility status of this project, the aim will be to inform the future design of a more complete economic analysis in a larger trial. In order to achieve this, we will explore the viability of conducting cost-effectiveness analyses through running exploratory analyses with the data gathered in the present project, and assess the completeness of our data collection processes. As part of this, we will present the relevant costs and health outcomes for both the intervention group and the wait-list control group.

For the costs, we will use data collected from the adapted CSRI at 6 months post randomisation. The primary focus will be on health and social care costs. Costs will include service use (health, social and voluntary services), intervention costs (such as speech and language therapist time, clinical supervision and specialist training), as well as considering informal care costs and costs to the individual (e.g. care provided by family members). Unit costs of resources used will be derived from routine sources locally where possible and from national sources such as the NHS reference costs. We will also refer to the unit costs for health and social care compiled by the Personal Social Services Research Unit ⁵³.

Health gains will be obtained from the answers to both the WEMWBS (primary outcome measure assessing well-being) and also the EQ-5D-5L instrument. The gold standard for economic evaluation is to use generic health state outcome measurements because these allow comparability across clinical areas. We will run two types of exploratory economic evaluation analysis. First, we will perform a cost-utility analysis using Quality Adjusted Life Years (QALYs) gained based on the answers to the EQ-5D-5L. Second, we will run

exploratory cost-effectiveness analysis based on the WEMWBS. We will provide an estimate of the relative cost-effectiveness of care received in the intervention group compared to the wait-list control group: this will be exploratory in nature given the feasibility status of the project.

6. Methods: monitoring

6.1 Data monitoring

Monitoring of the data will include confirmation of informed consent; source data verification; data storage procedures; accuracy of database entries. The Academic Supervisory Group will monitor the ongoing day-to-day collection of data on a monthly basis, and will advise on data monitoring processes. The TSC will also review evidence of data monitoring.

6.1.1 Stopping guidelines

There are no formal statistical criteria for stopping the trial early. Decisions to stop the trial early on grounds of safety or futility will be made by the TSC.

6.2 Harms

Adverse Events (AE) are any clinical change, disease or disorder experienced by the participant during their participation in the trial, whether or not considered related to the intervention being investigated. Adverse Events associated with participating in the study are considered unlikely. Such adverse events may include participants becoming distressed or anxious during assessment or therapy sessions, or during the in-depth interview.

Adverse events not related to the study may include:

Participants reveal to RAs or trial clinicians unrelated new medical issues which require an
assessment by a healthcare professional (e.g. fits or seizures, worsening visual difficulties,
increased frequency or severity of headaches, accidents or injuries such as falls).

Participant may score as 'distressed' on the GHQ-12 (scoring over 3) indicating low mood at any of
the assessment points; or may discuss symptoms of depression or anxiety during therapy sessions
or the in-depth interview.

Risks arising in the home or within the family.

If these adverse events do not lead to any of the outcomes listed a-g below, they will be considered non-serious. Their reporting is covered in the next section. RAs and trial clinicians will be trained on how to respond to such events (see 6.2.2 below).

Serious Adverse Events (SAEs) are considered unlikely in this project, however, they may still occur. Strokerelated events will not be reported as SAEs because these are expected within this population. An AE is considered a SAE if it results in one of the following outcomes:

- a) Death
- b) Suicide
- c) Life-threatening (i.e. with immediate, not hypothetical, risk of death at the time of the event, e.g. further stroke, cardiovascular event, serious infection)
- d) Requires in-patient hospitalisation (hospitalisation for elective treatment of a pre-existing condition is not included)
- e) Increased severe and persistent disability, where severe indicates significant deterioration in the participant's ability to carry out their activities of daily living; and persistent indicates four weeks continuous duration.
- f) Any other important medical condition, which, though not included in the above, may jeopardise the participant and may require medical or surgical intervention to prevent one of the outcomes listed.
- g) Any episode of deliberate self-harm

A SAE is considered a Serious Adverse Reaction (SAR) if the event is considered related to taking part in the study (e.g. is a consequence of receiving the intervention or taking part in the assessment sessions). A SAE is considered a Suspected Unexpected Serious Adverse Reaction (SUSAR) if the event is deemed as an unexpected reaction to participating in the study. Both SARs and SUSARs are considered highly unlikely in this study. If there is any doubt as to whether the AE is a SAE, SAR or SUSAR, a second opinion will be obtained from members of the Academic Supervisory Group in discussion with the CI.

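### Section 5.3.2 plans to count adverse reactions, but Section 6.2 defines no non-serious reaction, relatedness is judged only for SAEs, and the examples conflict on distress in therapy

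*Protocol*

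**What the plan says.** Section 5.3.2 of the Protocol commits to five counts: "Adverse events, adverse reactions, serious adverse events, serious adverse reactions and suspected unexpected serious adverse reactions will be summarised overall and by treatment group". It sends the reader to Section 6.2 for what these terms mean, and adds a between-group difference in event rates with a 95% confidence interval.

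Section 6.2 defines an AE broadly, "whether or not considered related to the intervention being investigated". Of AEs associated with taking part, which it considers unlikely, it says: "Such adverse events may include participants becoming distressed or anxious during assessment or therapy sessions, or during the in-depth interview". It then opens a second list with "Adverse events not related to the study may include". One item there reads "Participant may score as 'distressed' on the GHQ-12 (scoring over 3) indicating low mood at any of" the assessment points, and continues that a participant "may discuss symptoms of depression or anxiety during therapy sessions" or the in-depth interview. The section goes on to define SAE, SAR and SUSAR.

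Section 6.2.1 covers relatedness in its paragraph on SAEs: "The relationship of the event to the treatment (SAE or SAR) and expectedness of the event (SAR or SUSAR) may be assessed" by the staff member completing the form, after which the CI discusses the classification with at least two members of the Academic Supervisory Group. Non-serious AEs are reported to that group monthly and to the TSC annually. No relatedness judgement is mentioned for them.

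Section 7.4 lists the safety of the intervention among the things that guide the decision to progress to a definitive trial.

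**The concern.** The intervention is a talking therapy, and its main plausible harm is that mood worsens during or after sessions. Most such events would be non-serious. They fall in the class for which the Protocol promises a count of reactions but gives neither a definition nor a step that would identify one.

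The examples make this worse. One list treats distress in a session as associated with the study. The other places two closely related signals, symptoms voiced in therapy and a high GHQ-12 score at any visit, under a heading that declares them unrelated before anyone has looked at the case. Two clinicians seeing the same session could file it differently, and both could point to Section 6.2. At stake is whether the adverse-reaction figure that reaches the progression decision can be interpreted.

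**Working it through.** **1. What Section 5.3.2 counts, against what Sections 6.2 and 6.2.1 supply.**

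| Category counted | Defined in 6.2? | Relatedness step? |
|---|---|---|
| AE | Yes, regardless of cause | Not needed |
| Adverse reaction (non-serious) | No | None described |
| SAE | Yes, by outcomes a to g | Not needed |
| SAR | Yes, an SAE related to taking part | Yes, CI with at least two group members |
| SUSAR | Yes, an unexpected reaction | Yes, same discussion |

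One row is empty in both columns.

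**2. The two example lists side by side.** A participant becomes anxious while describing their anxiety in a therapy session. That fits the study-associated list (distress or anxiety in a session) and the not-related list (symptoms of anxiety discussed in a session). No rule separates them.

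The GHQ-12 item applies at every assessment point. At T1, before randomisation, therapy cannot be the cause of a high score. At T2, three months after randomisation, the intervention arm is at the end of its therapy period and therapy could be a cause. Both scores carry the same heading.

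**3. Is the count forced to any value?** The Protocol gives no expected number of adverse reactions, so there is no figure to reproduce. Suppose session distress is recorded as a reaction, as the first list allows, and affects a proportion p of the 16 treated in the intervention arm. The values of p are assumptions.

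- Expected people = 16p; chance of at least one = 1 − (1 − p)^16.
- p = 5%: 0.8 people, chance 0.56.
- p = 10%: 1.6 people, chance 0.81.
- p = 20%: 3.2 people, chance 0.97.

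The count is not forced to zero. If the same events are filed under the second list, they contribute nothing. The result therefore turns on filing as well as on what happened.

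**4. How well would the label-free comparisons show a worsening?** Inputs: 16 per arm (Section 3.6), and a background GHQ-12 distress rate of 45% in a comparable population (Section 6.2.2), used here only to gauge precision and assumed equal in both arms.

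- Half-width of the 95% interval for a difference in proportions = 1.96 × √(2 × 0.45 × 0.55 / n).
- n = 16: 1.96 × √(0.495/16) = 0.345, about ±34 points.
- After attrition, 32 × 0.85 = 27.2, which Section 3.6 gives as around 28. At 14 per arm: 1.96 × √(0.495/14) = 0.369, about ±37 points.

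**5. Are raw AE counts collected alike in the two arms?** Trial clinicians are among those who report AEs (Section 6.2.1), and before T3 only the intervention arm has therapy sessions. The wait-list arm has an extra assessment at T4 (Section 3.5). All-AE counts can therefore differ between arms for reasons of observation alone. GHQ-12 scores at T2 and T3 do not share this weakness, since both arms are assessed at the same visits by a blinded assessor.

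**The case against.** The other side has several good points.

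- The second list is introduced with wording that offers examples, so it is not a coding rule. Becoming distressed and disclosing existing symptoms can be different events. With background distress as common as Section 6.2.2 expects, most high GHQ-12 scores will have nothing to do with the study.
- A reader could build a definition by analogy with SAR: an AE related to taking part.
- All AEs are compared by arm whatever their label. GHQ-12 is also a secondary clinical outcome summarised by arm and time point (Sections 3.4.2 and 5.3.1), and the T3 and T4 interviews ask about well-being and the therapy.
- Relatedness judged by an unblinded CI is subjective.

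These points limit the consequence but leave the gap. Examples still steer the people filling in forms, the wording does not separate reaction from disclosure, and a definition by analogy still has no step that applies it. The randomised comparisons do protect against harm going unseen, though imprecisely.

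Three stronger readings are tempting and are not supported.

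- A reader might infer that adverse reactions will be near zero whatever happens. The study-associated list, and step 3 of the working, show otherwise.
- A reader might multiply 45% by the sample size and call the result misclassified harm. That rate is background prevalence, not an effect of therapy, and the GHQ-12 item also covers the visit before randomisation.
- A reader might take the word may in Section 6.2.1 to mean that SAE causality is optional. It governs only the staff member's entry on the form; the CI's discussion with at least two group members is stated as something that will happen.

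**Conclusion.** The point holds as an internal inconsistency that should be corrected. Section 5.3.2 promises a count that Sections 6.2 and 6.2.1 do not define or produce, and the examples conflict for distress in therapy. As written, the non-serious adverse-reaction count depends on who reports the event and would tend to omit therapy-related mood worsening. How many events would be omitted cannot be derived from the documents. A worsening could still appear in the all-AE comparison and the GHQ-12 summaries by arm, with a margin of roughly ±34 to ±37 points for the proportion distressed.

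This rests on two assumptions. First, the AE form, which is not shown, contains no relatedness judgement beyond what Section 6.2.1 describes. Second, the statistical analysis plan, also not shown, does not replace the definitions; Section 5.3.2 names Section 6.2 as their source, so the gap lies within the Protocol either way.

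**What to change.** 1. In Section 6.2, remove the not-related heading from the GHQ-12 and depression or anxiety items. List them as AEs whose relatedness is to be judged, so that the two lists no longer conflict.
2. In the same section, define an adverse reaction as an AE judged possibly related to the therapy or to study procedures.
3. In Section 6.2.1, have relatedness recorded for each non-serious AE at the monthly Academic Supervisory Group review that already takes place.
4. Keep the all-AE comparison by arm in Section 5.3.2 and report it alongside the adverse-reaction count.

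The cost is a few sentences, one field on the AE form and some minutes at an existing meeting. The judgement will be subjective and the CI knows the allocation, which is why the label-free comparison must stay. The reported number of adverse reactions may rise.
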